### 3.2 Subject Randomization and Blinding

### 3.2.1 Randomization Method

This study is a randomized study.

After providing due explanation to each prospective patient and his legal representative, the investigator or subinvestigator will obtain written informed consent/assent, and then prepare a screening log of patients whose legal representative consented to participate in the study in order to check the patient enrollment in the study. After confirming that the prospective patient is deemed eligible by meeting all of the inclusion criteria and none of the exclusion criteria, all necessary information will be entered the Interactive Web Response System (IWRS) and submitted to the Enrollment Center.

Upon completion of enrollment after confirmation of subject eligibility, the subjects will be randomly assigned to the low-dose group, high-dose group, or placebo group in a ratio of 1:1:1 via IWRS based on a dynamic randomization method (minimization method).

Data will be entered in accordance with the description in the IWRS procedure.

The subjects will be stratified by the following randomization adjustment factors:

- Age (between 5 and 6 years, 7 years or older)
- Presence or absence of concomitant steroid use

The above-mentioned enrollment and randomization will be centrally managed; after completion of the enrollment procedure, each subject will be assigned to a treatment group and given an investigational product number to be initially prescribed (for 6-week administration) by the enrollment system.

The investigational product numbers corresponding to subject randomization will be given and reported to the study site with instructions on the investigational product prescription via IWRS. For more detailed information, refer to the IWRS procedure.

If an investigational product not corresponding to the number given via IWRS is prescribed to a subject in error, the IWRS help desk must be notified immediately. In addition, the cause of the erroneous prescription of the investigational product must be recorded at the study site. If a subject receives the investigational product for a different treatment group due to an error in the investigational product number allocation or prescription, the subject will continue to receive the investigational product for the rest of the study period.

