# 4. Patient Inclusion/Exclusion and Subject Discontinuation Criteria

#### 4.1 Inclusion Criteria

Patients who meet all of the criteria below at the enrollment will be included in the study. The rationale is described in Section 14.3.

- (1) A legal guardian (legal representative) of a male pediatric patient with the ability to give consent provides written informed consent to participate in the study (whenever possible, informed voluntary assent should also be obtained personally from the patient after all information has been given in a way that suits the patient's level of understanding).
- (2) Patients with a diagnosis of dystrophinopathy as determined by a dystrophin genetic test or muscle pathology findings, symptoms or signs characteristic to DMD (e.g., proximal muscular weakness, waddling gait, Gowers sign), and progressive walking difficulty at the time of informed consent.
- (3) Patients aged 5 years or more at the time of informed consent
- (4) Patients weighing  $\ge$  7.5 kg and < 60 kg within 14 days before enrollment
- (5) Patients who can rise from the floor or a chair and walk by themselves at the screening test (confirmed by medical interview, actual performance, etc.), with 6MWD of 75 m or more (use of wheelchair in daily activities is permissible)
- (6) Patients who can stay in the hospital for the time period specified in the study
- (7) Patients who can continue with administration of the specified number of tablets
- (8) If the patient is receiving oral steroids for DMD treatment, he had begun the treatment more than 6 months before informed consent, and his symptoms remain stable with no change in the prescription-based dosage regimen of steroids within 3 months

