### 14.5 Rationale for Randomization Adjustment Factors

• Since DMD, a progressive muscular dystrophy, develops with increasing age, age was set as a randomization adjustment factor. The age classification (between 5 and 7 years, 7 years or older) was set by reference to the reports on a stratified analysis of 6MWD in the placebo

group administered a similar drug and on a 36-month natural course data in ambulatory patients with DMD. The presence or absence of concomitant steroid use was also set as a randomization adjustment factor because the concomitant use of steroid can considerably affect the efficacy evaluation.

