#### **17.1 Source Documents**

Source documents refer to original documents, data, and records (e.g., hospitalization records, medical records, test records, memoranda, checklists for subject evaluation, medication records, recorded data of automatic measuring instruments, CT image data, subject files, records retained at the Pharmacy Department, Inspection Department, and medical engineering departments involved in this study, IWRS-related materials, etc.).

Specific details of source documents for this study will be recorded in the list of source documents, etc. (or any documents to replace it) after preview with the investigator, and a copy of the list will be provided to the investigator.

Items listed below are "materials to be entered directly into the CRFs and regarded as source data."

- Diagnosis
- Presence or absence of previous medical history or concurrent illness that is considered to have a significant effect on the study in the opinion of the investigator or subinvestigator
- History of steroid use (age of initiation of use)
- Assessment of the presence or absence of abnormal change in blood pressure, pulse rate, body temperature, 12-lead ECG, or cardiac ultrasonography (echocardiography)
- Reasons for use of any concomitant medications or therapies (including steroids), their route of administration, and names or therapies and routes of administration of any drugs prescribed at another hospital
- Presence or absence of adverse events, names of the adverse events, severity (intensity), serious/non-serious, action concerning the investigational product, outcome, reason for completion of follow-up, and causal relationship to the investigational product
- Presence or absence of withdrawal/dropout and reason
- Comments

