#### **6.1** Analysis of the Primary Endpoint

The following analyses will be performed in the PPS and FAS:

The following analyses will be performed for the primary endpoint, defined as the change from baseline in 6MWD at Week 24: Analysis will also be conducted in the group combining the low-dose group and the high-dose group excluding the analysis of MMRM.

- A 2-sample t-test will be performed between each treatment group and placebo group. This analysis will be performed with and without the LOCF imputation. Analyses will also be conducted with the following baseline definitions.
  - (1) Analysis excluding the subjects for whom the value of (6MWD on Day 1 6MWD at screening)/6MWD at screening is 0.2 or higher or -0.2 or lower
  - (2) Analysis using the mean value of 6MWD on Day 1 and 6MWD at screening as the baseline value
- With respect to the above analysis, subgroup analysis will be conducted for the following items.

Subgroup analysis: Presence or absence of the history of steroid use, age category ( $\geq$ 5 years and <7 years, and  $\geq$ 7 years), and baseline 6MWD (<350 m, and  $\geq$ 350 m)

- The treatment effect will be estimated using the MMRM. The changes from baseline in 6MWD measured at other time points will also be included in this analysis. Covariates will be the assigned group, baseline value, time point, and the interaction term of the assigned group and time point.
- Using the MMRM, the dose relationship will be analyzed with treatment contrasts of (placebo group, low-dose group, high-dose group) = (-2 1 1), (-1 0 1), and (-1 -1 2). The changes from baseline in 6MWD measured at other time points will also be included in this analysis. Covariates will be the assigned group, baseline value, time point, and the interaction term of the assigned group and time point.
- For the above 2 analyses, analyses will be conducted in the PPS by adding age and the presence or absence of the history of steroid use to explanatory variables. In addition, subgroup analysis will be conducted for the following items.

Subgroup analysis: Baseline 6MWD ( $\leq$ 350 m, and  $\geq$ 350 m)

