#### Actual number of tablets

Dosing Rate =  $\frac{1}{(Criteria number of tablets (Administration number of days^{*1} \times Tablets/dose \times n Dose/day))^{*2}}$ 

\* To be induced from Day of last administration - Day of first administration + 1, because there is an allowable period for the day of last administration. The number of days will be calculated by subtracting 0.5 from the number of days of administration if administration is started in the evening on the day of first administration, and also by subtracting 0.5 from the number of days of administration if administration is terminated in the morning of the day of last administration.

\* If the dose is reduced during the study, the denominator for the dosing rate will be the sum of the number of days of administration before dose reduction  $\times$  tablets/dose before dose reduction  $\times$  twice/day and the number of days of administration after dose reduction  $\times$  tablets/dose after dose reduction  $\times$  twice/day.

- The Dosing Completed Rate of TAS-205 (proportion of subjects who were administered TAS-205 as in a specified schedule) will be calculated. The subjects will be the patients for whom the dosing rate is lower than 100%.
  - The presence or absence of concomitant medication and concomitant therapy (other than steroids) will be tabulated.
  - The presence or absence of the use of steroids will be tabulated.

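### Boys are minimised on concomitant steroid use, but every steroid subgroup and covariate in the SAP uses an undefined history of steroid use, so any former user would be allocated under one steroid status and analysed under the other.

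*SAP*

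**What the plan says.** Protocol 3.2.1 allocates boys "in a ratio of 1:1:1 via IWRS based on a dynamic randomization method (minimization method"), with two adjustment factors: age (5-6 years against 7 or older) and "Presence or absence of concomitant steroid use". Protocol 14.5 gives the reason for the second factor: "the concomitant use of steroid can considerably affect the efficacy evaluation".

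The SAP uses a different steroid variable in every subgroup and model that has one:

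- **Subgroups.** SAP 6.1 lists "Presence or absence of the history of steroid use, age category" and baseline 6MWD. The same list appears in 6.2.1(1) and 6.2.1(2).
- **Adjusted MMRMs.** SAP 6.1 repeats the 6MWD models in the PPS by "adding age and the presence or absence of the history of steroid use to explanatory variables". SAP 6.2.1(2) does the same for %MVI.
- **Exploratory ANCOVAs.** All three models in SAP 6.6 include history of steroid use as an explanatory variable.

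The SAP does not define history of steroid use. Protocol 17.1 names the CRF item as "History of steroid use (age of initiation of use"). Protocol Table 5-1 lists it separately from current medication. SAP 6.4 summarises history among the subject characteristics, and SAP 6.5 adds "The presence or absence of the use of steroids will be tabulated". SAP Table 3.1 lists the randomisation adjustment factors from IWRS as an analysis input.

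**The concern.** History of use and current use are different attributes, and they part company for a boy who took steroids and stopped. Such a boy can enrol: inclusion criterion (8) begins "If the patient is receiving oral steroids for DMD treatment, he had begun the treatment more than 6 months before informed consent", so it constrains only boys still on treatment, and no exclusion criterion mentions past use. Protocol 1.1 notes that adverse reactions to steroids can lead to dose reduction, regimen change or suspension, so former users are plausible.

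On the plain meaning of the two terms, a former user counts as absent for minimisation and as present in the analysis. Two things would be at stake. The present stratum would contain boys with no background steroid, which blurs any contrast by steroid status. The balance across the three arms that minimisation gives within steroid status would not carry over to the strata analysed. With 11 boys per arm, a few boys moving between strata is noticeable.

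**Working it through.** **Step 1. Compare the two adjustment factors.**

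| Factor | Minimisation (Protocol 3.2.1) | SAP subgroup (6.1, 6.2.1) | Same? |
|---|---|---|---|
| Age | 5-6 / 7 or older | 5 to under 7 / 7 or older | Yes |
| Steroid | Concomitant use | History of use | No |

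One factor carries over unchanged and the other does not. The SAP gives no reason.

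**Step 2. Who moves.** Let C be current users and F former users among N = 33 (3 x 11). Under criterion (8), current users of oral steroids for DMD began more than 6 months before consent, so all have a history.

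- Concomitant cut: present = C, absent = 33 - C.
- History cut: present = C + F, absent = 33 - C - F.
- Share of the history-present stratum that is off steroid: p = F / (C + F).

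The two cuts differ by exactly F boys.

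**Step 3. Size.** The plan states no figure to reproduce: 33 rests on feasibility, and neither C nor F is given. I assume C = 15 to 20 and F = 2 to 6.

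| C | F | p | Absent, concomitant | Absent, history |
|---|---|---|---|---|
| 20 | 2 | 2/22 = 9% | 13 | 11 |
| 15 | 2 | 2/17 = 12% | 18 | 16 |
| 20 | 4 | 4/24 = 17% | 13 | 9 |
| 15 | 4 | 4/19 = 21% | 18 | 14 |
| 20 | 6 | 6/26 = 23% | 13 | 7 |
| 15 | 6 | 6/21 = 29% | 18 | 12 |

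Divided by three arms, the absent stratum has 4.3 to 6.0 boys per arm by concomitant use. By history it has 3.7 to 5.3 with two former users, or 2.3 to 4.0 with six.

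**Step 4. Dilution.** Suppose former users respond like never-users and are spread evenly over the arms. The effect in the history-present stratum is then (1 - p) x E_on + p x E_off. Subtracting E_off gives (1 - p) x (E_on - E_off), so the contrast between strata shrinks by p, here 9% to 29%.

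**Step 5. Balance.** I simulated 33 boys minimised 1:1:1 on age and concomitant use, 2000 runs per scenario. Everything below is assumed: 30% aged 5-6, range-sum minimisation with a 0.8 biased coin, 50% or 70% current users, and the stated share of the remaining boys being former users.

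| Current | Former, of those not on steroid | Mean F | Present stratum: arms differ by 3 or more, concomitant / history | Absent stratum: some arm under 2 boys, concomitant / history |
|---|---|---|---|---|
| 50% | 0% | 0 | 9.1% / 9.1% | 0.1% / 0.1% |
| 50% | 10% | 1.7 | 10.8% / 22.0% | 0.0% / 0.9% |
| 50% | 25% | 4.0 | 8.6% / 35.7% | 0.2% / 5.8% |
| 50% | 50% | 8.2 | 8.0% / 42.5% | 0.1% / 39.5% |
| 70% | 0% | 0 | 9.9% / 9.9% | 9.7% / 9.7% |
| 70% | 10% | 1.0 | 9.2% / 15.2% | 9.7% / 20.8% |
| 70% | 25% | 2.5 | 10.0% / 23.6% | 9.2% / 44.4% |
| 70% | 50% | 4.9 | 8.9% / 29.9% | 9.5% / 81.9% |

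Cut by concomitant use, the chance of arms differing by 3 or more among users stays at 8% to 11%. Cut by history, it rises with the number of former users. With none, the two cuts are identical.

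**The case against.** The strongest reply is that the SAP never says a former user is coded as present. Protocol 17.1 only lists data that may be entered directly in the CRF, and Table 5-1 names the item without defining it. In SAP 6.4 history is the only baseline steroid variable and sits with an age category identical to the minimisation cut. The steroid line in 6.5 follows the tabulation of other concomitant medication and need not be a second definition of baseline status. Steroid history in the subgroup list may therefore be the minimisation factor loosely named. This stands as far as it goes: misclassification follows from plain meaning, not from a stated coding rule. It does not remove the need for a change, because if current use is meant the SAP should say so.

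A reader might also infer that the subgroups were set up to show whether TAS-205 works with and without background steroid, and so fail their purpose. The documents do not say that. Protocol 14.5 explains the factor for allocation only, and a subgroup need not be a minimisation factor: baseline 6MWD at 350 m is not one.

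The impact is also limited. The study is exploratory, multiplicity is not adjusted (SAP 3.4.5), and a stratum of about 4 to 6 boys per arm says little under either definition. Finally, SAP 7 refers to an appendix list of analysed items that is not in the available text, so the finding that no analysis uses the concomitant factor is confined to the SAP body. These points bear on severity. They do not explain why one adjustment factor was carried over and the other changed.

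**Conclusion.** The mismatch is established and reaches every steroid subgroup and steroid covariate described in the SAP body. Its effect is conditional. If former users enrol and history carries its plain meaning, the present stratum mixes boys on and off steroid and the strata are not those balanced by minimisation. Under the assumed 15 to 20 current and 2 to 6 former users, 9% to 29% of the present stratum is off steroid, and the absent stratum loses 2 to 6 boys. With no former users there is no effect.

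It would be tempting to conclude that boys will certainly be misclassified or that the trial's main result is compromised. Neither is supported. The number of former users is unknown, and the primary analysis (SAP 5) is summary statistics by treatment group with no steroid term. The unadjusted t-tests and the base MMRMs also contain no steroid variable. The point concerns supportive and exploratory analyses, and it should be corrected because the correction is simple.

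**What to change.** In SAP 6.1, 6.2.1(1), 6.2.1(2) and 6.6, define the steroid subgroup and covariate as concomitant steroid use at enrolment, as recorded in IWRS for the minimisation. Keep history of steroid use as a descriptive characteristic in 6.4, preferably split into current, former and never, so that the number of former users is visible.

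If the sponsor does want ever-use as an analysis variable, the SAP should define it, state how former users are coded, and present it as supplementary to the cut by the minimisation factor.

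The cost is SAP wording and the matching programming specification, best settled before the code is broken. The IWRS factors are already listed as an input in Table 3.1. No new data, visits or change to trial conduct are needed.

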## **3.4.6** Use of an "Efficacy Subset" of Patients

In this study, the analysis for efficacy evaluation will be conducted in the per protocol set (PPS). The analysis will also be conducted in the full analysis set (FAS) as supplementary analysis.

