- (2) The following analyses will be performed for each value measured in each motor function test (time to rise from the floor test, Timed 10-m walk/run test, Timed Up & Go test), measurement of muscle volume (skeletal muscle CT, BIA), lean body mass, quantitative muscle strength assessments (hip flexion/extension, knee flexion/extension, ankle extension/flexion), serum CK concentration (only the serum CK concentration during the hospitalization period will be used for the efficacy evaluation), and pulmonary function test (VC, FVC, FEV1.0, FEV1.0%): In the analysis of the muscle volume measurement (skeletal muscle CT) in the PPS, the subjects of the reference values will be excluded. See Table 10.1 Method to Derive %MVI (%) for derivation of %MVI (%) of the muscle volume measurement (skeletal muscle CT). In quantitative muscle strength assessments, the maximum values in the measurement without compensation will be used.
  - Summary statistics will be calculated at each time point for each treatment group.
  - Summary statistics for the change from baseline will be calculated, followed by a 2-sample t-test between each treatment group and placebo group at each time point. The data at Week 24 will be analyzed with and without the LOCF imputation.
  - With respect to the above 2 analyses, subgroup analysis will be conducted for the following items.

Subgroup analysis: Presence or absence of the history of steroid use, age category ( $\geq$ 5 years and <7 years, and  $\geq$ 7 years), and baseline 6MWD (<350 m, and  $\geq$ 350 m)

- The treatment effect will be estimated at each time point using the MMRM. The changes from baseline in the values measured at other time points will also be included in this analysis. Covariates will be the assigned group, baseline value, time point, and the interaction term of the assigned group and time point.
- Using the MMRM, the dose relationship will be analyzed at each time point with treatment contrasts of (placebo group, low-dose group, high-dose group) = (-2 1 1), (-1 0 1), and (-1 -1 2). Covariates will be the assigned group, baseline value, time point, and the interaction term of the assigned group and time point.

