- For the above 2 analyses, %MVI (%) of muscular amount measurement (skeletal muscle CT) will be analyzed in the PPS by adding age and the presence or absence of the history of steroid use to explanatory variables. In addition, subgroup analysis will be conducted for the following items. Subgroup analysis: Baseline 6MWD (<350 m, and ≥350 m)

- The time course by each time point will be plotted for each treatment group. Similarly, changes in the muscle volume measurement (skeletal muscle CT) from baseline in the PPS will be plotted.

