## **6.4** Subject Disposition and Characteristics

- (1) Subject disposition
  - The number of subjects randomized to each group will be tabulated in a manner so as to clarify attribution of subjects in each analysis set, and a summary and a list of subjects excluded from each analysis set will be provided with the reason for exclusion.
    - The presence or absence of important protocol deviations will be tabulated among the all enrolled patients. The types of deviations will be displayed together with the number of subjects.
    - The presence or absence of and the reasons for study discontinuation will be summarized among the all enrolled patients.
- (2) Subject characteristics
  - For each analysis set, excluding all enrolled patients, distribution of the following subject and disease characteristics will be summarized.
    - Demographic variables: Gender, race, age, age category (≥5 years and <7 years, and ≥7 years), height, body weight, presence or absence of previous medical history, and presence or absence of complication.
    - 2) Subject characteristics variables: Previous medical history, complication, presence or absence of diagnosis of DMD, diagnosis of DMD, presence or absence of the history of steroid use, history of steroid use, presence or absence of history of surgery, history of surgery, rehabilitation status, presence or absence of fitting of splint/insole, presence or absence of the use of wheel chair, 6MWD test, time to rise from the floor test, timed 10-m walk/run test, Timed Up & Go test

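### The treatment models leave out both minimisation factors, except in PPS-only models for 6MWD and CT %MVI

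*SAP*

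**What the plan says.** **Allocation.** Protocol 3.2.1 allocates 1:1:1 by minimisation on age in two classes (5-6 years; 7 or older) and "Presence or absence of concomitant steroid use". Protocol 14.5 justifies age by disease progression and steroids on the ground that "the concomitant use of steroid can considerably affect the efficacy evaluation".

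**Main analyses.** SAP 6.1 compares each dose with placebo by t-tests without covariates and by an MMRM, in PPS and FAS. For the MMRM, "Covariates will be the assigned group, baseline value, time point, and the interaction term of the assigned group and time point". The MODEL statement in SAP 8.3 agrees. SAP 6.2.1 treats the other efficacy measures the same way: "The treatment effect will be estimated at each time point using the MMRM", with the same covariate list.

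**Adjusted analyses.** For 6MWD, SAP 6.1 repeats the MMRM analyses in the PPS by "adding age and the presence or absence of the history of steroid use to explanatory variables". For CT, SAP 6.2.1 says that %MVI alone "will be analyzed in the PPS by adding age and the presence or absence of the history of steroid use to explanatory variables". No other adjusted treatment model is planned. The ANCOVAs in SAP 6.6 include age and steroid history but list no treatment term.

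**Variables.** SAP 6.4 lists age and its category separately ("Demographic variables: Gender, race, age, age category"). SAP Table 3.1 already imports the randomisation factors from the IWRS.

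**The concern.** Minimisation makes the arms more alike on the two factors than chance would. A model without those factors still counts their variance as residual noise, so its standard error describes a trial with less balance than this one has. If the factors are prognostic beyond baseline, intervals over-cover and tests reject too rarely. With 11 boys per arm, that is precision the trial can ill afford to lose.

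The PPS adjusted models cover only part of this. Nothing corresponds to them in the FAS. Of the measures listed in SAP 6.2.1, these have no adjusted model in either set: 3 timed tests + BIA + lean body mass + 6 strength measures + CK + 4 spirometry measures = 16. The other two CT measures in Protocol 11.4.1 (MVI and nMV_CT) also have none.

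The covariates that are added are not tied to the allocation. 'Age' could be continuous or the category. 'History of steroid use' is not defined and not equated with concomitant use. If it means any past or present use, the two steroid variables differ through former users. No eligibility criterion excludes former users, and no document shows that there are any.

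**Working it through.** The sample size is feasibility-based and no SD or effect size is given, so there is no planned precision figure to reproduce. The check asks how much wider the baseline-only interval is than the interval with both factors.

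**From the documents:** 33 boys, 11 per arm, three arms, two binary minimisation factors, baseline covariate, two-sided 95% intervals.

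**1. Approximation.** Let R² be the share of the variance left after baseline that the two factors explain, and suppose the balance is perfect. Residual df are 33 - 4 = 29 (three arms, baseline) without the factors and 33 - 6 = 27 with them. Then

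adjusted / unadjusted width ≈ √(1 - R²) × t(27) / t(29) = √(1 - R²) × 2.052 / 2.045.

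| R² | ratio | unadjusted excess |
|---|---|---|
| 0.1 | 0.952 | 5.1% |
| 0.2 | 0.897 | 11.4% |
| 0.3 | 0.839 | 19.1% |

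**2. Simulation of the allocation.** Assumed: 85% biased coin; age uniform from 5 to 11.67 years (70% aged 7 or older); 60% on steroids; R² split equally between the factors; no treatment effect; high dose v placebo; single-visit ANCOVA; 9,000 runs per cell. The age effect is either linear or a step at 7. Mean interval widths in SD units, with baseline not prognostic and independent of age:

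| | R² 0 | 0.1 | 0.2 | 0.3 |
|---|---|---|---|---|
| Linear: baseline-only | 1.760 | 1.764 | 1.772 | 1.772 |
| Linear: with IWRS factors | 1.776 | 1.702 | 1.628 | 1.546 |
| Excess | -0.9% | 3.6% | 8.8% | 14.6% |
| Step: baseline-only | 1.765 | 1.768 | 1.771 | 1.775 |
| Step: with IWRS factors | 1.781 | 1.685 | 1.587 | 1.485 |
| Excess | -0.9% | 4.9% | 11.6% | 19.5% |

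A second setting (nominal baseline R² 0.1, age-baseline correlation -0.5) was also run. Over both settings, at R² 0.1 / 0.2 / 0.3:

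- Excess width: 3-5 / 8-12 / 15-21%.
- Type I error, baseline-only model: 3.9-4.5 / 2.8-3.8 / 2.2-2.9%.
- Type I error, t-test: 3.4-4.6 / 2.5-3.7 / 1.8-2.9%.
- Type I error with the IWRS factors: 4.4-5.4%.
- True sampling SD of the estimate without the factors: within 0.5%, then 0.5-2.2% and 1.6-4.2% higher. The loss is therefore mostly in the reported interval, not in the estimate.

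With a 70% or 100% coin at R² 0.3, the excess is 14.0 or 15.2% (linear) and 18.8 or 19.6% (step).

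**3. Two-visit MMRM.** With REML, unstructured covariance and residual correlation 0.6, the excess is 3.5-5.2 / 7.9-11.6 / 13.2-18.7%, and -0.7% at R² 0. One cell (R² 0.1, step effect, Week 12 effect half that at Week 24) was not run.

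**4. Separate simulation with other assumptions.** Assumed: 60% aged 7 or older, 70% on steroids, factors independent of baseline, best-arm probability 1.0, 6,000 trials per setting. Baseline-only coverage is 96.2 / 96.6 / 97.8%. The excess width is 1.769/1.686, 1.773/1.587 and 1.774/1.480, that is 5 / 12 / 20%. With both factors, coverage is 94.4-95.4%. Under simple randomisation, baseline-only coverage stays near 95%, so the over-coverage comes from balancing on the factors and then omitting them.

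**5. The planned PPS adjusted model.** Read as continuous age plus history, its width relative to the IWRS-factor model at R² 0.1 / 0.2 / 0.3 is as follows. The shares of non-users who are former users are assumed.

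| Former users | Linear age effect | Step at 7 |
|---|---|---|
| 0% | 0.5 / 2 / 3.5% narrower | 2 / 3 / 5% wider |
| 25% | 1-1.5% wider | 3 / 6 / 9-10% wider |
| 50% | 2-3 / 3-4 / 4-5% wider | 4-5 / 8-9 / 12-14% wider |

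**The case against.** The strongest reply is that the plan already adjusts where it matters most. SAP 3.4.6 makes the PPS the efficacy set and the FAS supplementary, and the PPS has an adjusted 6MWD model. The primary analysis is summary statistics, and Protocol 14.1 reads efficacy from numerical trends without requiring significance. The error is conservative and no decision rule depends on interval width. This stands, and it limits the importance of the point.

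Second, every magnitude is assumed. At R² 0.05 the separate simulation gives only 1.765/1.729, about 2% excess. Protocol 14.5 supports age by reports on 6MWD and natural course, and offers nothing specific to CK, BIA, strength or spirometry. The simulations cover one and two visits, whereas Table 1 of the protocol schedules seven post-baseline visits for BIA and four for spirometry. This stands too: the direction is firm, the size for those measures is not.

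Third, 'age' is most naturally continuous, since the SAP uses a separate term for the category, and the steroid mismatch needs former users whom no document mentions. With none and a linear age effect, the planned PPS model is slightly better than the IWRS version. That is fair. The covariate wording is a request for definition; the case does not rest on it.

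None of this closes the gap in the FAS or in the secondary measures. Protocol 14.1 says muscle volume, lean body mass and strength were added because motor function alone may not be enough. Apart from CT %MVI, none of those has an adjusted model.

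**Conclusion.** The concern holds. The t-tests and main MMRMs omit both factors used to allocate. Adjusted treatment models exist only in the PPS, for 6MWD and CT %MVI, with two covariates not tied to the allocation factors. If the factors explain 10, 20 or 30% of the variance, the baseline-only intervals are about 3-5, 8-12 or 15-21% wider than they need be. If they explain nothing, there is nothing to gain. The estimates are unbiased and type I error is not inflated.

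The firm part is the FAS MMRMs and the secondary measures without an adjusted model. The gain over the planned PPS adjusted models is uncertain and may be zero or slightly negative. The sizes rest on assumed prognostic strength, age and steroid mix, and coin probability. In an exploratory trial with a descriptive primary analysis, this is a cheap improvement to consider, not a flaw that threatens the conclusions.

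**What to change.** - Add the IWRS age category and concomitant steroid use, as main effects, to the efficacy MMRMs in both FAS and PPS, including the secondary measures that now have no adjusted model.
- In the existing PPS adjusted models, use concomitant steroid use from the IWRS, state whether age is continuous or the category, and define history of steroid use. Keep the history version as a sensitivity analysis.
- Say whether the subgroup MMRMs by baseline 6MWD also carry the terms, since they have few boys per arm.
- Leave the t-tests as they are. Protocol 13.1.3.2 specifies them and names the MMRM without listing covariates, so a SAP edit before unblinding is enough.

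The cost is two terms in the MODEL statement, 2 degrees of freedom, and intervals about 1% wider if the factors explain nothing. The data are already in the IWRS transfer.
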